12.0 Data Management

The study database spreadsheets

- The databases will be maintained in the VAMC Charleston secure (V:) drive and accessed only by the Research Coordinator(s) and the PI.
- All data entered will be with the assigned codes.
- All shared data will be with the assigned codes.

Sample Size Estimation: The sample size of this study is 250 (Part 1) and 60 (Part 2) based on practical considerations and reasonable statistical power. Our inferences will be based on the determination of threshold on *p*-values to achieve a false discovery rate (FDR) of 10%. We anticipate that the large majority of genes will not be significant, but do not know the *p*-value threshold; we expect it to be between 0.001 and 0.01. This sample size estimation is consistent with the data analytic approaches discussed under Study Design.

The primary endpoint is to estimate PSA reduction between pre and post treatment. We expect 20% PSA reduction posttreatment with the standard deviation of 40%. With 60 patients, the 95% confidence interval for the estimated PSA reduction is 10% to 30%.

Statistical Analysis

All statistical analyses will be performed using SAS v. 9.4 or R statistical analysis packages. The overall PSA reduction rate and the corresponding 95% confidence interval and percentage of each core from 12 cores will be estimated. Basic descriptive statistics will be estimated for demographic at pretreatment and clinical variables (blood pressure, weight, hips and waist circumference, vitamin D level, blood sugar, cholesterol, kidney function and stress hormones) at pre and post treatment.

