4.0 Study Endpoints

We will be investigating Veterans who are undergoing prostate biopsy. If the Veterans are eligible and seek active surveillance as their treatment modality, they will be offered an opportunity to receive 4,000 IU Vitamin D supplementation as per previous protocol. Upon repeat biopsy (standard of care), they will have repeat RNA-seq analyses which will serve as further internal control. We will be measuring serum prostate specific antigen (PSA) as per standard of care recommendations. A blood sample for ancestry markers will be collected at the conclusion of the study.

Primary clinical endpoint: We will be assessing for clinical activity based on PSA changes, and investigating whether or not vitamin D supplementation results in a 20% decrease from baseline PSA.

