5.0 Inclusion and Exclusion Criteria/ Study Population

Males only, due to the limitation of the study to prostate tissue

Part 1

Inclusion Criteria

- a) Age: 50 - 75 years of age
- b) Scheduled to undergo a standard of care prostate biopsy because of an elevated PSA, an abnormal DRE (digital rectal exam) or other diagnostic procedure.
- c) Permission for investigators to follow subject's post biopsy diagnosis, treatment decision and follow/up care (including subsequent prostate biopsies).

Exclusion criteria:

Inability or unwillingness of subject to give informed consent

Part 2

Inclusion Criteria

- a) Prostate biopsy pathology report with diagnosis of prostate cancer
- b) Treatment recommendation and/or subject decision of active surveillance
- c) Agreement to take vitamin D₃ 4000 IU daily for approximately one year
- d) Standard of care repeat PSA at six months and surveillance (repeat) prostate biopsy after one year

Exclusion Criteria

- a) Initial testing of prostate biopsy core sample indicates non-viable RNA for further sequencing.
- b) Current vitamin D supplementation > 2000 IU daily
- c) Inability or unwillingness to continue as a participant in the study

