(Agilent Technologies, Palo Alto, CA). High-quality RNA will be divided into two de-identified-coded samples and forwarded for storage to the Principal Investigator's Laboratory at the Charleston VAMC. Only one of the two split samples will be bulk shipped to [name] Genomics Core Laboratory at City of Hope Comprehensive Cancer Center in Duarte, CA. for RNA-sequencing. 100-200 ng of total RNA will be used to prepare RNA-Seq libraries using the TruSeq RNA Sample Prep Kit (Illumina, San Diego, CA) following the protocol described by the manufacturer. Paired end cluster generation will be performed on the cBot as described by the manufacturer (Illumina, San Diego, CA). Clustered RNA-seq libraries will be paired end sequenced with 250 cycles on a HiSeq2500 (Illumina, San Diego, CA). This new instrument acquired recently by MUSC generates up to 1 Tb per run, with data yields typically containing 80% greater than Q30, 2 x 100 bp read length. The "paired end" approach will be employed for the RNA-seq experiments, wherein a single long read is sequenced for 100 nucleotides at both ends. In addition to providing digital mRNA profiling, this strategy will permit tracking alternate splice junctions, insertions and deletions, and facilitate transcriptome assembly in these prostate cells and experimental groups.

Each sample will be sequenced to a depth of 100 million reads. Adapters will be trimmed by Trimmomatic (38). Alignment and annotation will be performed using DEseq2 (39), Edge R (40, 41) and the Tuxedo Suite comprising Bowtie2, Tophat2 and Cufflinks2 (42). As we are interested in applying RNA-seq as a discovery tool, the Tuxedo Suite will facilitate the identification of alternative splicing events, allele-specific expression, and rare and novel transcripts in these mRNA data sets.

Sample Size Estimation: The sample size of this study is 250 (Part 1) and 60 (Part 2) based on practical considerations and reasonable statistical power. Our inferences will be based on the determination of threshold on *p*-values to achieve a false discovery rate (FDR) of 10%. We anticipate that the large majority of genes will not be significant, but do not know the *p*-value threshold; we expect it to be between 0.001 and 0.01.

The primary endpoint is to estimate PSA reduction between pre and post treatment. We expect 20% PSA reduction post-treatment with the standard deviation of 40%. With 60 subjects, the 95% confidence interval for the estimated PSA reduction is 10% to 30%.

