14.0 Withdrawal of Subjects

Participation in Part 1 of this study may be a single study visit, or if the subject agrees to another prostate core sample obtained as standard of care approximately 12 to 18 months after his initial prostate biopsy, participation will be two study visits. Participation in Part 2 will include an initial visit (when inclusion criteria are met), at six months for PSA and vitamin D level and a final visit for repeat prostate biopsy, allostatic load measurements, vitamin D level and ancestry marker. Subjects may withdraw their decision to participate at any time after signing the consent forms. This includes the use of any specimens that are not already exhausted by laboratory analysis.

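### The primary PSA estimate is a simple pre/post mean that leaves the scheduled six-month PSA unused; a two-visit model would protect it against PSA-related loss at almost no cost

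*Combined protocol and SAP*

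**What the plan says.** Section 4.0 gives the clinical aim as "investigating whether or not vitamin D supplementation results in a 20% decrease from baseline PSA". Sections 10.0 and 12.0 restate it for sample size: "The primary endpoint is to estimate PSA reduction between pre and post treatment". None of the three places names a visit.

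The whole analysis plan for this endpoint is one sentence in Section 12.0: "The overall PSA reduction rate and the corresponding 95% confidence interval and percentage of each core from 12 cores will be estimated". It assigns no role to an intermediate PSA and has no rule for a missing one.

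Two PSAs follow the start of supplementation, at six months and at about one year. Both are in Section 11.0 (Part 2, item 6, chart review) and in the Appendix 1 flowchart. Two other sections are less complete:
- The Part 2 inclusion criteria in Section 5.0 ask for "Standard of care repeat PSA at six months and surveillance (repeat) prostate biopsy after one year".
- Section 14.0 describes follow-up as "at six months for PSA and vitamin D level and a final visit for repeat prostate biopsy, allostatic load measurements, vitamin D level" and does not list PSA at the final visit.

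On precision, Section 10.0 says "With 60 subjects, the 95% confidence interval for the estimated PSA reduction is 10% to 30" percent. Sixty is also the number to be enrolled in Part 2. Section 14.0 adds: "Subjects may withdraw their decision to participate at any time after signing the consent forms".

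**The concern.** A simple pre/post mean can use only men who have the post-treatment value. If that value is the one-year PSA, a man who is followed to six months and then lost drops out of the estimate, although his six-month PSA is in the chart.

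This does little harm if loss is unrelated to PSA. On active surveillance, though, a rising PSA is a plausible reason to leave. If that happens, the mean is taken over men who did better, and the error runs toward the hoped-for reduction. With one arm, there is no comparison group in which the same selection could cancel. The six-month PSA carries information about the men who leave, and the plan does not use it.

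**Working it through.** **Inputs from the plan.** Expected reduction 20%, SD 40%, n = 60, 95% interval (Sections 10.0 and 12.0).

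**Assumed, because the documents are silent.** Loss of 10% or 20% (6 or 12 of 60 men). Normally distributed changes. Correlation 0.5 to 0.8 between six-month and one-year change. In the main pattern, the chance of loss doubles for each SD of six-month rise.

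**Step 1: the plan's own interval.** 20 ± 1.96 × 40/√60 = 20 ± 10.1, or 9.9 to 30.1. This reproduces 10% to 30%. With t quantiles, the half-width is 10.3 at n = 60, 10.9 at n = 54 and 11.6 at n = 48. Loss alone therefore costs 0.6 to 1.3 points of half-width.

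**Step 2: bias of the completers-only mean.** If k men are lost and their six-month change lies on average m SDs above the cohort mean, the one-year mean among those who remain is too favourable by about

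ρ × 40 × m × k/(60 − k).

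Simulation (40,000 trials per setting) gives these overstatements in points:

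| Loss | ρ = 0.5 | ρ = 0.8 | Coverage of the 95% interval |
|---|---|---|---|
| 10% (6 men) | 1.4 | 2.2 | 94% to 93% |
| 20% (12 men) | 2.8 to 2.9 | 4.6 | 92% to 87% |

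The 2.8 and 2.9 differ only by simulation error. Solving the formula for m shows how mild this pattern is. At 10% loss, 1.4/(0.5 × 40 × 6/54) = 0.63. At 20% loss, 4.6/(0.8 × 40 × 12/48) = 0.58. The lost men average about 0.6 SD above the cohort. Against the expected 20% reduction, the overstatement is 1.4/20 = 7% to 4.6/20 = 23%.

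**Step 3: the two-visit estimate on the same data.** Regress one-year change on six-month change among completers, with slope b. Then evaluate at the six-month mean of all men who have that PSA:

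one-year mean of completers + b × (six-month mean of all − six-month mean of completers).

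Remaining bias, in points (where two values are shown, they are for ρ = 0.5 and 0.8):

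| How loss arises | Loss | Completers only | Two-visit |
|---|---|---|---|
| Depends on six-month PSA | 10% | 1.4 / 2.2 | at most 0.1 |
| Depends on six-month PSA | 20% | 2.9 / 4.6 | at most 0.1 |
| Same, half lost before six months | 20% | 2.9 / 4.7 | 1.3 / 2.1 |
| Depends on one-year PSA | 10% | 2.8 | 2.1 / 1.0 |
| Depends on one-year PSA | 20% | 5.8 | 4.4 / 2.2 |

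When loss depends on the one-year value, the share of bias removed runs from (5.8 − 4.4)/5.8 = 24% to (2.8 − 1.0)/2.8 = 64%.

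**Step 4: when the model does not matter.** If loss is unrelated to PSA, neither estimate is biased, and the half-width at 20% loss goes from 11.6 to between 11.4 and 10.9. With no loss, the two estimates are identical.

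**The case against.** **The visit is largely identifiable.** A reader might infer that the post-treatment PSA could equally be either visit, so that the result could be picked after both are seen. The documents do not support that strength.
- Supplementation lasts about a year and a second bottle is dispensed at six months, so the six-month PSA is on-treatment.
- Section 12.0 uses the same pre/post wording for blood pressure, waist and hip measurements and cholesterol, which the flowchart schedules only at baseline and about one year.
- The sentence that estimates PSA reduction also estimates core percentages, and follow-up cores exist only at the repeat biopsy.
- Section 5.0 is an eligibility list and Section 14.0 a summary of participation. Their omission of a one-year PSA does not contradict the schedule.

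This stands, short of proof: vitamin D level is in the same pre/post list and is also measured at six months. What remains is a missing phrase.

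**Sixty is a target.** Section 6.0 calls it a goal, and the sample size is said to rest on practical considerations. This also stands. The interval is right for 60 men, and the loss of precision deserves only a note.

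**The bias rests on assumptions, and the plan limits loss.** Coordinators schedule both PSA visits, and missed follow-up appointments trigger an alert to the clinic. A reader might equate stopping capsules with a missing PSA. That does not follow, because PSA is standard of care, is read from the chart, and Part 1 entry requires permission to follow "post biopsy diagnosis, treatment decision and follow/up care (including subsequent prostate biopsies". The real gaps are withdrawn consent, missed follow-up and a move to definitive treatment. How often these occur, and whether they track PSA, is not stated.

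**Leaving out a mid-treatment value is an ordinary choice in a descriptive estimate.** That is fair. The case for change is that the value is already collected and costs nothing to use.

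**Conclusion.** The point holds as a cheap improvement of minor to moderate weight. As written, the primary analysis would by default discard a man who has a six-month PSA but no one-year PSA. Under a mild PSA-related loss pattern, the completers-only mean overstates the reduction by about 1.4 to 2.2 points at 10% loss and 2.8 to 4.6 points at 20% loss. A two-visit model removes nearly all of this if the six-month PSA explains loss, and about a quarter to two-thirds if loss follows the one-year PSA.

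Only n = 60 and the SD of 40% come from the plan. The loss rate, the correlation and the link between loss and PSA are assumptions. Without that link there is no bias.

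Harsher patterns can be built: 6.1 points if half of a 20% loss are the largest six-month risers, and 11.0 if all are (both at correlation 0.8). Nothing in the documents suggests selection that sharp, so these are not a fair measure of the problem. Nor do the documents support reading the 10% to 30% interval as wrong.

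**What to change.** 1. In Section 12.0, name the one-year PSA, drawn before the repeat biopsy, as the primary post-treatment value. Carry the same wording into Sections 4.0 and 10.0, and list the one-year PSA in Sections 5.0 and 14.0.
2. Estimate the one-year change from a repeated-measures model using the six-month and one-year changes of every man who starts supplementation and has at least one follow-up PSA. Report completers only as a sensitivity analysis.
3. Keep using chart PSAs from men who stop capsules, unless they withdraw consent. How PSAs after definitive treatment are handled is the sponsor's estimand choice and should simply be stated.
4. Report how many men have no follow-up PSA. As a note beside the 10% to 30% interval, give the half-width of 10.9 to 11.6 points expected at 10% to 20% loss.

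The model needs one defined baseline PSA for each man. The flowchart collects none at the Part 2 baseline visit and points to the pre-biopsy value. That is a separate matter, but the same paragraph should settle it.

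The cost is wording and a little analysis work: no extra men, visits or blood draws. The downside is an added assumption that loss is explained by the six-month PSA. The model removes only part of the bias if loss follows later PSA, does not help men with no follow-up PSA, and changes nothing if no one is lost.

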13.0 Provisions to Monitor the Data to Ensure the Safety of Subjects

This study requires an initial visit (Part 1): consent process plus collection of an extra prostate biopsy tissue core for study analysis.

If the pathology report indicates prostate cancer and the subject's treatment decision is active surveillance, he may continue participation to Part 2. Data collected in this phase will be: demographics, blood pressure, heart rate, hip/waist ratio, allostatic load blood results, one survey, a repeat prostate biopsy core collection, vitamin D levels, PSAs, RNA-seq of prostate core samples, and serum ancestry markers.

All samples will be labeled with the assigned de-identified code (except for samples analyzed by the VAMC laboratory services which require name and last four of the social security number). VAMC laboratory results will be entered into the research database with the assigned code. All shared data will be under the assigned codes.

During each study visit, an adverse or unanticipated study-related event is unlikely, but may occur. Therefore, if an adverse event occurs, it will be reported as required to the Institutional IRB, VA R&D, and all other oversight committees and organizations. The Attending Urologist in the VA Urology Clinic at the time of the event will evaluate the subject and the event and schedule follow-up medical intervention as needed.

If, upon review of the study required blood results, an abnormal result is reported by one of the laboratories, the subject's primary health care provider will be notified via the VA CPRS electronic records system for evaluation, possible treatment and follow-up.

14.0 Withdrawal of Subjects

Participation in Part 1 of this study may be a single study visit, or if the subject agrees to another prostate core sample obtained as standard of care approximately 12 to 18 months after his initial prostate biopsy, participation will be two study visits. Participation in Part 2 will include an initial visit (when inclusion criteria are met), at six months for PSA and vitamin D level and a final visit for repeat prostate biopsy, allostatic load measurements, vitamin D level and ancestry marker. Subjects may withdraw their decision to participate at any time after signing the consent forms. This includes the use of any specimens that are not already exhausted by laboratory analysis.

15.0 Risks to Subjects

1. Venipuncture: the risks of drawing blood include temporary discomfort from the needle stick and bruising, fainting could occur.
2. Collection of an extra prostate tissue (punch) core from the peripheral area of the prostate will not significantly create more health risk to the subject than the standard 12 (punch) core collection incurred during the routine procedure. Prostate biopsies are done under local anesthesia, and the extra prostate biopsy may cause 7% more discomfort as a result. The collection from this area will not interfere with the Pathologist's analysis and diagnostic process.

3. Loss of Confidentiality of protected health information (unlikely side effect). A Master List with contact information is required as Good Clinical Practice for dissemination of new information and follow-up care. This Master List will be maintained by the Research Coordinator(s) on the VA secure (V:) drive. Only the Research Coordinator(s) and the PI will have access to this list. The Master List will also serve as the link in identifying each subject to his assigned code.
4. Taking vitamin D₃ supplementation at 4000 IU daily poses no risk to the subjects. This dose is well within the recommended doses by the Endocrinology Society and Institute of Medicine.
5. Some questions in the Social Determinants survey may make subjects uncomfortable or upset. Subjects will be instructed to skip any questions that they do not wish to answer.
6. Genetic Research. The RNA-sequencing will analyze transcriptional profiles and biological pathways on the molecular level in prostate tissue. It is not identifying specific genes and an individual's predisposition to a particular diagnosis or disease process. The ancestry markers will be analyzed for racial origin/significance only. No DNA analysis for disease identifiers will be performed.

16.0 Potential Benefits to Subjects or Others

A direct benefit may not be gained by the participants. However, if measuring gene expression in prostate tissue specimens provides molecular biomarker(s) for assessing the effects of circulating levels of vitamin D on cancer, it will be extremely important in determining treatment options for future cases of prostate cancer at time of diagnosis. Preliminary studies have demonstrated evidence of decreased positive biopsy cores after one year of supplementation at 4000 IU daily. Also, RNA-seq analysis has demonstrated improvement in inflammatory profiles in prostate tissue in men supplemented with vitamin D₃.

17.0 Sharing of Results with Subjects

- The allostatic load laboratory results analyzed in the VAMC laboratory will automatically be entered into the VA electronic record and can be viewed by each participant's Health Care Provider and shared as needed with the subject.
- Vitamin D serum levels (baseline, six months and exit) will be reported to the subject. The subject's Primary Health Care Provider will be notified for follow-up as needed at the end of Part 2.
- The blood pressure, heart rate and waist/hip measurements will be shared with each subject when they are obtained.
- The survey is self-completed and each subject will know the information his contains.
- The RNA-seq analyses will be published at the completion of the study. All results will remain de-identified.
- The ancestry markers will not be shared with the subjects.

18.0 Drugs – vitamin D supplementation

FDA IND# 77,839 was originally granted to [name] in 2007 for an open-label clinical study designed to assess the effect of vitamin D₃ on subjects with early-stage prostate cancer. This clinical trial will be conducted under the same IND, which has been transferred to the PI, [name]. The vitamin D₃ (cholecalciferol) is manufactured by JR Carlson Laboratories, Inc., [name]. JR Carlson Laboratories will manufacture soft gel capsules containing 4000 IU of vitamin D₃ for the study. The study medication will be shipped to the research pharmacy of the Ralph H. Johnson VA Medical Center where it will be stored and dispensed as per standard procedure.

References

- 1) http://www.cancer.org/docroot/CRI/content/CRI_2_4_1X_What_are_the_key_statistics_for_prostate_cancer_36.asp
- 5) Schwartz GG. Vitamin D and the Epidemiology of Prostate Cancer. *Semin Dial*; 18: 276-289, 2005
- 8) Feldman, Pike, and Adams, Eds. *Vitamin D*, 3rd edition. San Diego, Academic Press, 2011.
